6.3. Lifestyle Restrictions

There are no lifestyle restrictions.

6.3.1. Meals and Dietary Restrictions

There are no meals or dietary restrictions.

6.3.2. Caffeine, Alcohol, and Tobacco

There are no caffeine, alcohol, and tobacco restrictions, other than those for a subject's inclusion and any local restrictions whilst the subject is in the clinic.

6.3.3. Activity

There are no restrictions on activity.

6.4. Screen Failures

Screen failures are defined as participants who consent to participate in the clinical study but are not subsequently randomized. A minimal set of screen failure information is required to ensure transparent reporting of screen failure participants to meet the Consolidated Standards of Reporting Trials (CONSORT) publishing requirements and to respond to queries from regulatory authorities. Minimal information includes demography, screen failure details, eligibility criteria, and any serious adverse events (SAEs).

Individuals who do not meet the criteria for participation in this study (screen failure) may be rescreened. Rescreened participants should be assigned a new subject number.

7. TREATMENTS

Study treatment is defined as any investigational treatment(s), marketed product(s), placebo, or medical device(s) intended to be administered to a study participant according to the study protocol.

7.1. Treatments Administered

Study Treatment Name:	ELLIPTA placebo DPI	DISKUS placebo DPI	HandiHaler DPI and placebo Capsules	Turbuhaler placebo DPI
Dosage formulation:	Placebo DPI with two strips with 30 blisters per strip. First strip: lactose monohydrate Second strip: lactose monohydrate blended with magnesium stearate	Placebo DPI with one blister strip containing lactose monohydrate.	DPI with placebo capsules containing lactose monohydrate	Placebo DPI containing lactose monohydrate
Route of Administration	Oral Inhalation	Oral Inhalation	Oral Inhalation	Oral Inhalation
Dosing instructions:	As directed	As directed	As directed	As directed
Packaging and Labelling	Study Treatment will be provided in the appropriate container and will be labelled as required per country requirement.	Study Treatment will be provided in the appropriate container and will be labelled as required per country requirement.	Study Treatment will be provided in the appropriate container and will be labelled as required per country requirement.	Study Treatment will be provided in the appropriate container and will be labelled as required per country requirement.
Manufacturer	GSK	GSK	Boehringer Ingelheim	AstraZeneca
Device	NA	NA	HandiHaler	NA

7.1.1. Medical Devices

- Other medical device (not manufactured by or for GSK) provided for use in this study is HandiHaler Dry Powder Inhaler

- Any extra instructions for medical device will be provided in the Study Reference Manual.

7.2. Method of Treatment Assignment

All participants will be centrally randomized using an Interactive Web Response System (IWRS). Before the study is initiated, the log in information & directions for the IWRS will be provided to each site.

Participants will be assigned in equal numbers to one of four sequences for the sub-study they are included on, in accordance with the randomization schedule generated by Clinical Statistics, prior to the start of the study and using validated internal software.

The possible sequences for each sub study are shown in Table 1 and Table 2

Table 1 Sub Study 1 Treatment Sequences

Sequence	Period 1	Period 2	Preference Questionnaire
A	ELLIPTA	DISKUS + HandiHaler	1
B	DISKUS + HandiHaler	ELLIPTA	2
C	ELLIPTA	DISKUS + HandiHaler	2
D	DISKUS + HandiHaler	ELLIPTA	1

Table 2 Sub Study 2 Treatment Sequence

Sequence	Period 1	Period 2	Preference Questionnaire
E	ELLIPTA	Turbuhaler + HandiHaler	3
F	Turbuhaler + HandiHaler	ELLIPTA	4
G	ELLIPTA	Turbuhaler + HandiHaler	4
H	Turbuhaler + HandiHaler	ELLIPTA	3

Study treatments will be dispensed at the study visit summarized in SOA

7.3. Blinding

This is an open-label study; however, the order of treatment and preference questionnaire answered by a participant will be assigned using an IWRS. The site will contact the IWRS prior to study treatment administration for each participant. The site will record the treatment assignment on the applicable case report form, if required. Potential bias will be reduced by randomising the order of treatment and the preference questionnaire version answered by subjects.

7.4. Preparation/Handling/Storage/Accountability

- The investigator or designee must confirm appropriate temperature conditions have been maintained during transit for all study treatment received and any discrepancies are reported and resolved before use of the study treatment. Details of transit and storage conditions for study treatments will be included in the SRM.
- Only participants enrolled in the study may receive study treatment and only authorized site staff may supply study treatment. All study treatments must be stored in a secure, environmentally controlled, and monitored (manual or automated) area in accordance with the labeled storage conditions with access limited to the investigator and authorized site staff.
- The investigator, institution, or the head of the medical institution (where applicable) is responsible for study treatment accountability, reconciliation, and record maintenance (i.e., receipt, reconciliation, and final disposition records).
- Further guidance and information for the final disposition of unused study treatment are provided in the Study Reference Manual.
- Under normal conditions of handling and administration, study treatment is not expected to pose significant safety risks to site staff.

7.5. Treatment Compliance

Participants receive study treatment only at the clinical site and they will receive study treatment directly under supervision of the investigator or designee.

The date and time of each dose administered in the clinic will be recorded in the source documents.

7.6. Concomitant Therapy

A detailed history of previous and ongoing COPD medications, in particular any types of inhalers used to deliver these medications for the previous 24 months from V0, should be recorded in order to inform on the subject's inclusion.

This is a single visit study, and the subject should continue to take their usual COPD and other medications through the conduct of the study.

However, any medication or vaccine (including over-the-counter or prescription medicines, vitamins, and/or herbal supplements) that the participant is receiving at the time of enrolment or receives during the study must be recorded along with:

- reason for use
- dates of administration including start and end dates
- dosage information including dose and frequency

The Medical Monitor should be contacted if there are any questions regarding concomitant or prior therapy.

7.7. Treatment after the End of the Study

There is no active treatment; this is a single visit, placebo only study and participants will not receive any specific post study treatments.

8. DISCONTINUATION CRITERIA

8.1. Discontinuation of Study Treatment

Not applicable as this is a single-visit study with no active treatment; all subjects will receive placebo treatment only.

8.1.1. Liver Chemistry Stopping Criteria

Not applicable as this is a single-visit study with no active treatment; all subjects will receive placebo treatment only. .

8.1.2. QTc Stopping Criteria

Not applicable as this is a single-visit study with no active treatment; all subjects will receive placebo treatment only.

8.2. Withdrawal from the Study

- A participant may withdraw from the study at any time at his/her own request, or may be withdrawn at any time at the discretion of the investigator for safety, behavioural, compliance or administrative reasons.
- If the participant withdraws consent for disclosure of future information, the sponsor may retain and continue to use any data collected before such a withdrawal of consent.
- This is a single visit, placebo only study, if a subjects withdrawals during this single visit there are no assessments that would need to be completed following withdrawal.

8.3. Lost to Follow Up

Not applicable as this is a single visit study.

9. STUDY ASSESSMENTS AND PROCEDURES

- Study procedures and their timing are summarized in the SoA.
- Protocol waivers or exemptions are not allowed
- Immediate safety concerns should be discussed with the sponsor immediately upon occurrence or awareness to determine if the participant should continue or discontinue study treatment.
- Adherence to the study design requirements, including those specified in the SoA, is essential and required for study conduct.

- All screening evaluations must be completed and reviewed to confirm that potential participants meet all eligibility criteria. The investigator will maintain a screening log to record details of all participants screened and to confirm eligibility or record reasons for screening failure, as applicable.
- Procedures conducted as part of the participant's routine clinical management (e.g., to confirm diagnosis of COPD) and obtained before signing of ICF may be utilized for screening provided the procedure met any protocol-specified criteria and was performed within the time frame defined in the SoA.
- Prior to randomisation, at V1, all assessments to confirm inclusion at V0 will be completed. The details of these assessment are provided in the SoA

9.1. Efficacy Assessments

[figure not shown]
9.1.1. Assessment of Errors in Use of Device

Within each sub-study, subjects will be randomised for the order of treatment. One treatment will require subjects to demonstrate use of a single inhaler (ELLIPTA), while the other treatment will require the subject to demonstrate use of 2 inhalers (DISKUS-HandiHaler in Sub Study 1 or Turbuhaler-HandiHaler in Sub Study 2).

Subjects will be provided with the relevant section of the PIL, explaining correct use, for each inhaler they are to be tested on. The critical and over all errors per inhaler and how these have been defined are included in Appendix 2.

The errors listed will be in aligned with the correct use information from the respective PILs, in a checklist for each inhaler and these will be provided to HCPs for scoring errors during the study conduct. The checklists will be provided in the Study Reference Manual.

Figure 2 depicts the process flow for assessing inhaler use errors and further details are provided, for each treatment, in Section 9.1.1.1 and Section 9.1.1.2.

Figure 2 Assessment of errors in use for each DPI tested**9.1.1.1. Assessment of ELLIPTA error in use**

Subject will be asked to read the patient instruction leaflet for ELLIPTA and then demonstrate ELLIPTA use. Any errors (critical or non-critical) made by the subject while using the ELLIPTA will be recorded by the HCP on the checklist provided. If the subject makes no errors, this will also be recorded by the HCP, and there will be no further assessments. If the subject makes any error in the use of the ELLIPTA, the HCP will provide instruction in the correct use of the ELLIPTA to the subject. The subject will then demonstrate ELLIPTA use again. If the subject makes no errors, this will be recorded by the HCP and there will be no further assessments. If the subject again makes errors in the use of the ELLIPTA any errors will be recorded by the HCP. The HCP will again provide instruction in the correct use for the final time, following which the subject will then demonstrate ELLIPTA use one final time. Any errors made during this demonstration will be recorded. There will be no further assessments. In total, the HCP can provide instruction in the use of the inhaler up to two times.

9.1.1.2. Assessment of DISKUS-HandiHaler in Sub Study 1, or Turbuhaler-HandiHaler in Sub Study 2, for error in use

Subjects will be provided with 2 inhalers and 2 PILs dependent on which sub study they are included in.

Subjects should be tested on each DPI provided consecutively, they will be tested in the following order for each sub study.

- Sub Study 1: DISKUS followed by HandiHaler

- Sub Study 2: Turbuhaler followed by HandiHaler

Subjects will be asked to read the patient instruction leaflet for the first DPI (DISKUS or Turbuhaler) and then demonstrate first DPI use. Any errors (critical or non-critical) made by the subject while using the first DPI will be recorded by the HCP on the checklists provided. If the subject makes no errors, this will also be recorded by the HCP and there will be no further assessment for this first DPI. If the subject makes any error in the use of the first DPI, the HCP will provide instruction in the correct use of the inhaler to the subject. The subject will then demonstrate inhaler use again. If the subject makes no errors, this will also be recorded by the HCP and there will be no further assessments for this DPI. If the subject again makes errors in the use of the DPI, the HCP will record the errors and provide instruction in correct use for the final time. The subject will then demonstrate use of first DPI for one final time. Any errors or correct use after this demonstration will be recorded, and there will be no further assessments for this DPI. In total, the HCP can provide instruction in the use of the first DPI up to two times.

This assessment will then be repeated with HandiHaler.

9.1.1.3. Time Taken to Use Device

Time taken to use the device will be recorded as follows:

- T1: the time from when the subject starts to read the patient instruction leaflet until they have completed demonstration of device use (i.e., with no investigator support).
- T2: the time from when the HCP starts to instruct subject until correct use is demonstrated (up to a maximum of two attempts only).
- T1+T2: the time from when the subject starts to read the patient information leaflet until correct use is demonstrated (up to a maximum of three attempts, once after reading the PIL and following instruction, up to 2 times, by HCP).

The HCP will start recording (clock start) the time from when T1 begins and will stop when device use has been demonstrated. The clock re-starts when T2 begins and stops once correct use has been demonstrated, or when three failed attempts have been made. Note: T2 includes the time used by the investigator for re-instructing the Subjects throughout.

For subjects who demonstrate correct inhaler use after reading the PIL, T2 will be 0.

9.1.2. Assessments of Preference

After completing the errors in use assessment for both treatments, the HCP will ask the subject questions from the assigned preference questionnaire. The wording of the questionnaires is included in Appendix 3.

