2. SCHEDULE OF ACTIVITIES (SOA)

Visit Number	V0	V1	Notes
Study Day	1	1	V0 can take place on the same day as V1. V1 should be completed no later than 30 days after consent.
Procedure:			
Screening Assessments			Completed prior to randomisation
Written informed consent	X		Informed consent may take place prior to V0 for logistical reasons. Subjects should be included and randomised within 30 days of providing consent.
Subject demography	X		Age, height, weight, year of birth, sex, ethnicity and geographic ancestry will be recorded
Medical/disease history including Chronic Obstructive Pulmonary Disease (COPD)	X		Subject will have a medical history of COPD, previously confirmed by spirometry.
Concomitant medication history including COPD Therapy History	X		Current concomitant medication will be recorded. A minimum COPD therapy history for the preceding 2 years from inclusion will be recorded
Inclusion/exclusion criteria	X		All criteria must be met prior to randomisation at V1
Study Assessments			Completed once a subject is included on study
Randomisation		X	Randomised to treatment order and preference questionnaire
Assess the number of inhaler errors (critical and overall) on each treatment after reading the Patient information leaflet (PIL) for Inhaler tested		X	No instruction is provided by the Health Care Professional (HCP) for this assessment.
Assess the number of inhaler errors (overall and critical) on each treatment after each of 2 attempts following instruction by HCP			If a subject cannot show correct use after reading the PIL, then the HCP has up to 2 attempts to instruct the subject to attain this.

Visit Number	V0	V1	Notes
Teaching-Training Time for each inhaler includes the following: 
 The amount of time taken to read the patient information leaflet and demonstrate inhaler use The amount of time taken to be given instruction by the HCP on use of the inhaler and demonstrate inhaler use The total amount of time taken to demonstrate inhaler use 		X	
 First assessment is attempt one, including time to read PIL and demonstrate use. Second assessment will be time for HCP to correct errors and subject to show use for up to 2 more attempts The Cumulative time for all assessments needed by subject and any HCP instruction to demonstrate no errors will also be captured.
Preference Questionnaire		X	Subject will complete version of Preference Questionnaire they have been randomised to.

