6.2. Exclusion Criteria

Participants are excluded from the study if any of the following criteria apply:

CONCURRENT CONDITIONS/MEDICAL HISTORY
1. Asthma: Subjects with a current diagnosis of asthma. Subjects with a prior history of asthma are eligible if they have a current diagnosis of COPD.
CONCOMITANT MEDICATIONS
2. Recent experience with the ELLIPTA inhaler: Subjects who used any ELLIPTA inhaler (e.g., RELVAR ELLIPTA, ANORO ELLIPTA, ARNUITY ELLIPTA, INCRUSE ELLIPTA, participated in a clinical study of GW685698, GW642444, GSK573719 [fluticasone furoate, vilanterol, umeclidinium bromide], or any combination thereof, or placebo in an ELLIPTA inhaler study) within 24 months prior to Visit 0.
3. Recent experience with any capsule inhaler: Subjects who used any capsule system inhaler (e.g. Spiriva HandiHaler, Seebri/Ultibro Breezhaler, or participated in a clinical studies of these, including placebo inhalers) within 24 months prior to Visit 0.
4. Dependent on which sub-study a subject is included on they should not have any recent experience, within 24 months of V0 of the following inhaler for the sub study included on: 
 • Sub Study 1: DISKUS inhaler (e.g. Seretide DISKUS or placebo DISKUS) • Sub Study 2: Turbuhaler (e.g. Symbicort Turbuhaler or placebo Turbuhaler)
RELEVANT HABITS
5. Drug/alcohol abuse: Subjects with a known or suspected alcohol or drug abuse at Visit 1 which in the opinion of the investigator could interfere with the subject's proper completion of the protocol requirement

CONTRAINDICATIONS
6. Drug/Food Allergy: A history of hypersensitivity to any components of the study inhaler (e.g., lactose, magnesium stearate). In addition, subjects with a history of severe milk protein allergy that, in the opinion of the study physician, contraindicates participation will also be excluded.
DIAGNOSTIC ASSESSMENTS AND OTHER CRITERIA
7. Investigational Product: Subjects who have received an investigational drug and/or medical device within 30 days of entry into this study (Screening/Visit 1), or within five drug half-lives of the investigational drug, whichever is longer
8. Inability to Read: In the opinion of the investigator, any subject who is unable to read and/or would not be able to complete a questionnaire and understand verbal instructions.

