12.3. Appendix 3: Inhaler Preference Questionnaires

Inhaler Preference Questionnaire Version 1

Instructions: Please complete the following questions related to the treatments you used during this study. Check only one response for each question.

1. Which treatment do you prefer based on the number of steps needed to take your COPD medication?
 - DISKUS and HandiHaler
 - ELLIPTA
 - No preference

2. Which treatment do you prefer for taking your COPD medication?
 - DISKUS and HandiHaler
 - ELLIPTA
 - No preference

Inhaler Preference Questionnaire Version 2

Instructions: Please complete the following questions related to the treatments you used during this study. Check only one response for each question.

1. Which treatment do you prefer based on the number of steps needed to take your COPD medication?
 - ELLIPTA
 - DISKUS and HandiHaler
 - No preference

2. Which treatment do you prefer for taking your COPD medication?
 - ELLIPTA
 - DISKUS and HandiHaler
 - No preference

Inhaler Preference Questionnaire Version 3

Instructions: Please complete the following questions related to the treatments you used during this study. Check only one response for each question.

1. Which treatment do you prefer based on the number of steps needed to take your COPD medication?
 - Turbuhaler and HandiHaler
 - ELLIPTA
 - No preference

2. Which treatment do you prefer for taking your COPD medication?
 - Turbuhaler and HandiHaler
 - ELLIPTA
 - No preference

Inhaler Preference Questionnaire Version 4

Instructions: Please complete the following questions related to the treatments you used during this study. Check only one response for each question.

1. Which treatment do you prefer based on the number of steps needed to take your COPD medication?
 - ELLIPTA
 - DISKUS and HandiHaler
 - No preference

2. Which treatment do you prefer for taking your COPD medication?
 - ELLIPTA
 - DISKUS and HandiHaler
 - No preference

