2.3. Study Design

Overview of Study Design and Key Features	

The flowchart illustrates the study design process. It starts with V0 (COPD patients screened for inclusion). A green arrow indicates that V0 and V1 can be completed on the same day. The process then moves to V1, where subjects receive their first treatment. This is followed by an assessment for inhaler errors (critical and overall) on Treatment 1, including reading the PIL(s) and receiving up to 2X instruction from the HCP. This is followed by the second treatment, another assessment for inhaler errors on Treatment 2, and a final V1 assessment where the subject completes a preference questionnaire. Below this, two sub-studies are detailed. Sub Study 1 compares ELLIPTA (Treatment option 1) to DISKUS + HandiHaler combination (Treatment option 2). Sub Study 2 compares ELLIPTA (Treatment option 1) to Turbuhaler + HandiHaler combination (Treatment option 3). Each sub-study involves a PIL, a stopwatch, and the respective inhaler combinations. Preference questionnaires (PREF 1, 2 for Sub Study 1; PREF 3, 4 for Sub Study 2) are completed after each treatment.
	

Design Features
	
The study will be conducted as a multi-centre, randomised, open-label, placebo-device, cross-over study, with a 2x2 complete block design.
 
It will comprise of two sub studies:
 
 • Sub-study 1 will compare ELLIPTA (Treatment option 1) to DISKUS + HandiHaler combination (Treatment option 2) • Sub-study 2 will compare ELLIPTA (Treatment option 1) to Turbuhaler + HandiHaler combination (Treatment option 3). 
The study has 2 visits (V0 and V1) and both can be completed on the same day. Each sub-study may run independently or in parallel of the other sub study. Each will start dependent on the availability of the placebo DPIs required for that sub-study. The data from the 2 sub studies may be reported independently and as each sub study completes and the data for that sub study have been cleaned. The database will be locked when all of the sub-studies have completed and all data are cleaned.

Dosing
	
 • Not applicable as this is a placebo study.

Overview of Study Design and Key Features				
Treatment Assignment	Sub-study 1 Treatment Sequences			
	Sequence	Period 1	Period 2	Preference Questionnaire
	A	ELLIPTA	DISKUS + HandiHaler	1
	B	DISKUS + HandiHaler	ELLIPTA	2
	C	ELLIPTA	DISKUS + HandiHaler	2
	D	DISKUS + HandiHaler	ELLIPTA	1

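### The protocol gives two modes for the preference questionnaire, asked by the HCP or completed by the subject; settle on self-completion, and correct Version 4 first

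*Protocol*

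**What the plan says.** Protocol section 9.1.2, the procedural section for this endpoint, describes an interview: "the HCP will ask the subject questions from the assigned preference questionnaire". It refers to Appendix 3 for the wording.

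Two other places in the protocol describe self-completion:

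- The note in the Schedule of Activities: "Subject will complete version of Preference Questionnaire they have been randomised to". SAP Appendix 2 repeats this row.
- The instruction at the top of all four versions in Appendix 3: "Please complete the following questions related to the treatments you used during this study. Check only one response for each question".

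On bias, protocol section 7.3 states "This is an open-label study" and then names its controls: "Potential bias will be reduced by randomising the order of treatment and the preference questionnaire version answered by subjects". Versions 1 and 2 differ only in which treatment is printed first.

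On analysis, protocol section 10.4.1 and SAP section 8.1.2.5 plan a CMH test for each of the two preference questions, taking account of the order of inhaler use, with p-values reported. Neither the questionnaire version nor the mode of administration enters the test. The mock preference listing in SAP Appendix 12 has no field for mode.

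**The concern.** There are two separate issues.

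The first is consistency. A site that follows section 9.1.2 will interview; a site that follows the Schedule of Activities or the form will hand over paper. The two sets of answers would be pooled with nothing to tell them apart.

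The second is bias. Preference is a subjective answer given by someone who knows which devices were used. Under section 9.1.2 it would be given aloud to the HCP role, which under sections 9.1.1.1 and 9.1.1.2 has just scored the subject on each device and, where there were errors, taught its use. No separate interviewer is required and no script is mentioned. Tone, prompting or a wish to please could move answers. If they move towards the same product in both treatment orders, the result looks exactly like a genuine preference.

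**Working it through.** **Where the mode is stated**

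| Place | Who acts |
|---|---|
| Protocol 9.1.2 | HCP asks |
| Protocol Schedule of Activities (repeated in SAP Appendix 2) | Subject completes |
| Protocol Appendix 3, instructions on each version | Subject completes and checks a box |
| Protocol 6.2, exclusion 8 | Excludes "any subject who is unable to read and/or would not be able to complete a questionnaire and understand verbal instructions" |

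The first row conflicts with the next two. The fourth fits either mode, because it covers both completing a form and following speech, but it does mean that enrolled subjects should be able to complete the form. No passage resolves the conflict.

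**What the safeguards cover**

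Randomising the version balances which treatment is listed first. It acts on position, not on a pull towards a named product.

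The CMH test works on the score in SAP section 11.5.4. Let δ be the proportion choosing ELLIPTA minus the proportion choosing the comparator, the same in both orders. The mean score is −δ when ELLIPTA is used first and +δ when it is used second. The test compares these means, a difference of 2δ. A tendency to favour the device used last adds the same amount to both means and cancels. A pull towards one product changes δ itself and does not cancel.

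**Illustration of size (assumed shifts)**

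The documents give no figure for interviewer influence, so there is nothing to reproduce. Inputs: 72 subjects per sub-study (protocol 5.2), split 36 and 36 by order. The remaining inputs are assumptions: no true preference, with ELLIPTA/comparator/none at 50/50/0 or 40/40/20, and a net shift towards ELLIPTA. A shift towards the comparator gives the same rejection rates.

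Two ways of producing the shift were simulated:

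- A fraction f of all non-ELLIPTA answers moves to ELLIPTA. From 40/40/20, δ = (0.4 + 0.6f) − 0.4(1 − f) = f. From 50/50/0, δ = (0.5 + 0.5f) − 0.5(1 − f) = f.
- A fraction x of all subjects moves from comparator to ELLIPTA, so δ = 2x.

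The denominators differ, so a 5% shift means δ = 5 points in the first case and 10 points in the second. On the scale of δ the results agree:

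| Net margin added (δ) | Answers out of 72 | Rejection rate, two-sided 5% |
|---|---|---|
| 0 | 0 | about 4–5% |
| 5 points (f = 5%) | 72 × 0.05 = 3.6 | about 6–8% |
| 10 points (f = 10% or x = 5%) | 72 × 0.10 = 7.2 | about 12–16% |
| 20 points (f = 20% or x = 10%) | 72 × 0.20 = 14.4 | about 38–48% |

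Hand check at 10 points from 50/50/0: z = δ√72/√(share expressing a preference) = 0.10 × 8.485/1 = 0.85. The rejection rate is Φ(0.85 − 1.96) + Φ(−0.85 − 1.96), about 13.6%, against 12.5% simulated.

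**Version 4**

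Protocol Table 2 assigns Version 4 to sequences F and G of Sub-study 2. Its comparator option in Appendix 3 reads DISKUS and HandiHaler, although those subjects used Turbuhaler and HandiHaler. With equal allocation to four sequences this is 2/4 of Sub-study 2, or 72 × 2/4 = 36 of 72 evaluable subjects. An interviewer might correct the name aloud; a subject completing the form alone would see a device that was not tested.

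**The case against.** The two wordings can be read together. An HCP could put the printed questions while the subject's choice is ticked, and the Schedule of Activities note is mainly about which version applies. That is a fair reading, but it is only one reading, and the protocol does not state it.

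The support for self-completion is also narrower than a count of places suggests. The SAP row copies the protocol's. A sentence in SAP section 2.3 saying that the subject completes the form appears to be a machine description of a figure, and it is given no weight here.

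A reader might infer several stronger things that the documents do not support:

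- *That an interview defeats the randomised option order.* Section 9.1.2 ties the HCP to the assigned version and to the Appendix 3 wording. Reading the options verbatim in that order keeps the randomisation. The order is lost only if that is not done, and the protocol does not explicitly require it.
- *That the same individual scores, teaches and then asks.* The documents name a role, not a person, and subjects who make no errors receive no teaching.
- *That answers would move towards ELLIPTA by a known amount.* Nothing shows the direction or the size. The rejection rates above also assume no true preference, whereas protocol section 3.2 cites earlier data favouring ELLIPTA.
- *That self-completion removes all such bias.* The study stays open-label and the form still goes back to staff, so a wish to please would partly remain.

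What stands is the unresolved mode, and an avoidable route for live influence on a subjective endpoint.

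**Conclusion.** The inconsistency is real and lies on the face of the protocol: section 9.1.2 against the Schedule of Activities and the form. It allows mixed data collection, and under the interview reading it allows interviewer influence that neither stated control nor the planned test would remove. The size of any effect is unknown. The illustration shows only that a net pull of 5 points barely exceeds the nominal rate while 20 points would matter, under assumed splits and no true preference. The two secondary preference items are affected; the primary critical-error endpoint is not. This is a cheap improvement to a secondary endpoint, not a threat to the trial's main conclusion.

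**What to change.** Amend section 9.1.2 to agree with the Schedule of Activities and the form. The subject reads and completes the assigned version without discussion. Staff hand it over, check it for missed boxes and record any help given. Any help is limited to reading the questions and options verbatim in the printed order. Repeat this in the Study Reference Manual.

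Before any subject uses it, correct Version 4 so that both questions name Turbuhaler and HandiHaler. The order matters: moving to self-completion while the misprint stands would make that problem worse.

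If the sponsor prefers to keep an interview, the protocol should require verbatim reading in the assigned order, preferably by staff who did not train the subject, and the other passages should be aligned to that mode. This keeps the option order but leaves some interviewer influence.

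The cost is a minor amendment, which under Appendix 4 needs ethics committee approval before implementation, and an occasional missed box to catch at collection. No change to visits, sample size or analysis is needed.
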